4.3.1.2.3 Vital Signs

Descriptive summaries for vital signs (systolic blood pressure, diastolic blood pressure, body temperature, pulse/heart rate, and respiration rate) will be presented for each visit starting at baseline (as defined in Section 4.1.1.2). Changes from baseline to each post baseline visit will also be presented.

Participant data listings of vital sign data will be provided.

4.3.1.2.4 Electrocardiograms

Electrocardiograms will be conducted at specific visits only. On Day 30, the ECGs will be conducted twice (pre-dose and 6 hours post dose).

All reporting for ECG data will be presented for central lab ECG results only. Descriptive summaries for ECG data (HR, PR interval, QRS duration, QT interval, corrected QT interval [QTcF, Fridericia correction], and RR) will be presented at each visit starting at baseline (defined in Section 4.1.1.2). Changes from baseline to each post baseline visit will also be presented.

If the RR is not collected it will be derived as follows: $RR = (60/HR)$.

Change from baseline for QTcF and uncorrected QT will be classified as follows:

- ≤ 30 msec or > 30 msec
- ≤ 60 msec or > 60 msec

Absolute postbaseline QTcF and uncorrected QT interval will be classified as follows:

- ≤ 450 msec or > 450 msec
- ≤ 480 msec or > 480 msec
- ≤ 500 msec or > 500 msec

Frequency counts and percentages will be tabulated for change from baseline and absolute post baseline QTcF values at each visit starting at baseline; participant listings will identify records where participant data falls into these regions. These summaries will also be presented for minimum and maximum post baseline values. The analysis of extreme values (e.g., maximum and minimum post baseline values) will be based on all post baseline assessments whether scheduled or unscheduled.

The number and percentage of participants with the following overall ECG results will also be tabulated at each visit. Shift tables for baseline to maximum post baseline overall ECG results, based on the three categories below will be provided. This analysis of extreme value shifts (e.g., maximum post baseline values) will be based on all post baseline assessments whether scheduled or unscheduled.

- Normal
- Abnormal, not clinically significant (NCS)
- Abnormal, clinically significant (CS)

All ECG data will be presented in data listings.

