b In order to minimize blood loss in participants, samples to be drawn for screening should be collected not less than 28 days prior to samples drawn on Day 1.

c Visits for Days 2, 60, 120, and 150 may be conducted at the clinic or as at-home telehealth visits. During at-home telehealth visits, home-health nurses will collect the required blood and urine samples and perform an assessment of vital signs. The Investigator will contact the participant's caregiver via telephone and/or video conference to assess the general well-being of the participant and determine if any adverse events have occurred. The Investigator must affirm that nedosiran may be administered prior to administration.

d The Investigator will contact the participant's caregiver via telephone and/or video conference to assess the general well-being of the participant and determine if any adverse events have occurred.

e After the first 2 injections of nedosiran, visiting nurses or caregivers will administer SC injections at home for those months at which a study-site visit is not required. The total dose will be based upon body weight recorded on study Day 1. For participants < 6 months of age at Screening, the dose will be adjusted at Day 90 to capture changes in weight; no other dose adjustments are allowed.

f Parental informed consent (and minor assent, if applicable per local regulations) is required prior to initiation of screening procedures.

g Participant eligibility (with the exception of clinical laboratory testing) will be re-confirmed prior to administration of study intervention on Day 1.

h PH history to include 12-month history of stone events, or as applicable for those less than 12 months of age (Section 8.1.3).

i To include vitamin B6 (pyridoxine), if applicable.

j Participants without documented genotyping must provide a DNA sample for testing. For participants who weigh ≤ 11 kg, PH genotyping will be performed via buccal swab; for all other participants, while genotyping via buccal swab is recommended to reduce blood sample volumes, genotyping performed via whole blood sample is allowed.

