### **8.2.3. Vital Signs**

Body temperature, pulse rate, respiratory rate, and blood pressure will be assessed.

Blood pressure and pulse measurements will be assessed in the supine position with a completely automated device. Manual techniques will be used only if an automated device is not available. An age-appropriate cuff size should be used for blood pressure measurements.

Blood pressure and pulse measurements should be preceded by at least 5 minutes of rest for the participant in a quiet setting without distractions (e.g., television, cell phones).

Temperature will be obtained in degrees Celsius (°C) via the same method throughout the study, pulse rate will be counted for a full minute and recorded in beats per minute, and respirations will be counted for a full minute and recorded in breaths per minute. Note that when a 12-lead ECG is performed at the same time as vital signs, heart rate should be taken from the ECG.

If multiple assessments are due at the same time point, PK sampling should be performed at the nominal time point, with the preferred order of assessments ECG, vital signs, PK, and then other assessments.

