### **8.2.4. Electrocardiograms**

Standard 12-lead ECGs will be performed with the participant in the supine position, after the participant has rested comfortably for 10 minutes. The parameters assessed will be rhythm, ventricular rate, PR interval, QRS duration, QT interval, and corrected QT interval (QTcF, Fridericia correction). The Investigator or designee is responsible for reviewing the ECG(s) to assess whether the results are within normal limits and to determine the clinical significance of the results. These assessments will be recorded on the eCRF.

Standardized ECG acquisition equipment will be provided to all clinical trial sites at the start of the trial, to ensure parity across all sites. All ECG data will be transmitted to a stand-alone imaging vendor, where qualified personnel will perform central overread of all ECG readouts. The end-to-end process of centralized ECG acquisition and overread is detailed in a separate

DCR-PHXC-203 Imaging Review Charter (Cardibase). Site personnel will be trained in the processes relating to ECG acquisition and transmission. Sites that have completed training for a similar Dicerna-sponsored study within the past 2 years are not required to repeat ECG training.

If multiple assessments are due at the same time point, PK sampling should be performed at the nominal time point, with the preferred order of assessments ECG, vital signs, PK, and then other assessments.

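### ECG heart rate and pulse are shown only as raw values and raw change, so in the few infants normal slowing is mixed into the Day 90 and Day 180 results; a low-priority gap in a descriptive safety display

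*SAP*

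**What the plan says.** **Heart rate on the ECG.** SAP 4.3.1.2.4 states: "Descriptive summaries for ECG data (HR, PR interval, QRS duration, QT interval, corrected QT interval [QTcF, Fridericia correction], and RR) will be presented" by visit, and then "Changes from baseline to each post baseline visit will also be presented". SAP 4.3.1.2.3 plans the same two displays for pulse, with plain listings.

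**Cut-offs and extremes.** In SAP 4.3.1.2.4, numerical categories are set only for QT and QTcF. The sentence "These summaries will also be presented for minimum and maximum post baseline values" follows the QTcF frequency tables and refers to them. The ECG listings flag only the QT and QTcF regions. The other extreme-value table concerns the whole tracing, graded normal, abnormal not clinically significant or abnormal clinically significant: "Shift tables for baseline to maximum post baseline overall ECG results, based on the three categories below will be provided". It does not separate out rate.

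**Age.** Safety tables are split by age group, with 0 to <2 years the youngest (SAP 4.1.2 and 4.3.1.2). A paper on normal limits for the paediatric ECG is reference 8 in SAP 6, but no analysis section applies it.

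**Timing.** After Day 1, ECGs fall on Days 30, 90 and 180. At those visits pulse adds little that is independent: "Note that when a 12-lead ECG is performed at the same time as vital signs, heart rate should be taken from the ECG" (Protocol 8.2.3). Separate pulse readings come from the visits without an ECG: "Visits for Days 2, 60, 120, and 150 may be conducted at the clinic or as at-home telehealth visits", and at home visits "home-health nurses will collect the required blood and urine samples and perform an assessment of vital signs" (Protocol Table 1, footnote c).

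**The concern.** Infant heart rate may fall with age. Baseline is one fixed pre-dose value (SAP 4.1.1.2) and there is no control arm, so raw change is the sum of any drug effect and maturation. Age-group rows separate one child from another but do not remove the change within a child over six months.

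The SAP handles comparable problems elsewhere. Laboratory results get shifts to maximum and minimum against normal ranges, with abnormal values identified in the listings (SAP 4.3.1.2.2). The oxalate-to-creatinine ratio is re-analysed relative to an age-tailored upper limit because of maturation (SAP 4.2.3). Heart rate and pulse get neither treatment. At stake is whether the infant rows at Days 90 and 180 can be read at face value.

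**Working it through.** The documents contain no heart-rate figure, so there is nothing to reproduce. The calculation below shows how large the mixing could be.

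**Inputs from the documents.** About 20 completers: 3 under 1 year, 10 aged 1 to 5, 7 aged 6 to 11 (Protocol 1.1). Visit days and repeat readings come from Protocol Table 1 and footnotes n and o.

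**Assumptions, not in the documents.** Normal heart rate falls linearly over 180 days by D bpm: 0 to 20 under 1 year, 0 to 4 at 1 to 5 years, 0 to 2 at 6 to 11 years. The drug raises heart rate by a constant 10 bpm.

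**1. Raw change in infants** = 10 - D × (fraction of 180 days elapsed).

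| Visit | Fraction | D = 0 | D = 10 | D = 20 | D that hides the rise fully |
|---|---|---|---|---|---|
| Day 2 | 1/180 | +10 | +9.9 | +9.9 | 1,800 |
| Day 30 | 1/6 | +10 | +8.3 | +6.7 | 60 |
| Day 90 | 1/2 | +10 | +5 | 0 | 20 |
| Day 180 | 1 | +10 | 0 | -10 | 10 |

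The last column is 10 / fraction. Pulse on Days 120 and 150 lies between the Day 90 and Day 180 rows.

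**2. Older children at Day 180.** Ages 1 to 5: 10 - 4 = +6 up to +10. Ages 6 to 11: 10 - 2 = +8 up to +10.

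**3. The SAP's 0 to <2 row at Day 180.** With 3 infants and k children aged 1 to <2 (k is not stated), the mean fall is (3D + k·d)/(3 + k), where d is the fall at 1 to <2 years.
- D = 10, d = 2: k = 0, 2, 4 gives falls of 10, 6.8, 5.4, so the row shows 0, +3.2, +4.6.
- D = 20, d = 4: falls of 20, 13.6, 10.9, so the row shows -10, -3.6, -0.9.

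**4. All 20 completers at Day 180.** With falls of (20, 4, 2) in the three age bands, the mean fall is (3×20 + 10×4 + 7×2)/20 = 114/20 = 5.7, so the overall row shows +4.3. With (10, 2, 1) it is 57/20 = 2.85, so +7.15.

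**5. Precision of an age-referenced mean in 3 infants.** The 95% half-width is t(0.975, 2 df) × SD/√3 = 4.303 × SD/1.732. For an assumed SD of change of 10 to 15 bpm this is 24.8 to 37.3 bpm, wider than the largest assumed bias of 20 bpm.

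**6. Sensitivity of a count above a limit (one reading).** For a 98th-centile limit and an assumed between-child SD of 10 to 20 bpm, a 10 bpm rise moves the share above the limit from 2% to P(Z > 2.054 - 10/SD) = 14.6% to 6.0%. The chance of seeing 0 of 3 infants above it is 0.854³ = 0.62 to 0.940³ = 0.83.

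**7. False flags from a maximum.** There are nine scheduled post-dose vital-sign readings: Day 1 at 6 hours, Day 2, Day 30 twice, and Days 60, 90, 120, 150 and 180. With no drug effect, the chance that a child's maximum exceeds a 98th-centile limit is 2% if readings are fully correlated and 1 - 0.98⁹ = 16.6% if independent. That is 0.4 to 3.3 of 20 children, before unscheduled records and the lower limit.

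**The case against.** A reader might infer that the plan would miss tachycardia in infants. The documents do not support that. Protocol 8.2.4 states "The Investigator or designee is responsible for reviewing the ECG(s) to assess whether the results are within normal limits", and central overread follows. Absolute values are shown by visit and age group, and three infants can be read line by line in the listings. Adverse-event reporting and review by the Safety Review Committee also apply. Day 2, and the pre-dose and 6-hour pairs on Days 1 and 30, are little affected by maturation. These routes can find individual cases. None is specified as an age-referenced summary of rate, so the gap in the display stands.

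A reader might also infer a known cardiac signal. In the earlier placebo-controlled study one of 23 nedosiran participants had a tachycardia SAE, judged possibly related by the investigator and unrelated by the sponsor; no clinically important trends were seen (Protocol 2.2.3.1). The PH3 study showed no treatment-related trends in vital signs or ECG, the monkey studies showed no adverse cardiovascular effects, and heart rate is not an event of special interest here. This is a weak prior.

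Three further objections carry weight:
- The slowing is assumed, and the range includes zero, where nothing is hidden.
- With 3 infants an age-referenced mean is very imprecise, so less bias does not bring reliable detection.
- SAP 1 sends unlisted table specifications to mock outputs that are not among the documents. If the tables are there, the SAP need only name them.

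Masking should not be read across to PR or QRS; nothing here shows it.

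**Conclusion.** The point holds in limited form. As the SAP is written, heart rate and pulse have no age reference, extreme-value table or listing flag, and raw change in infants at Days 90 and 180 mixes drug effect with maturation. A rise could be understated, or reversed if slowing is large: under the assumed 0 to 20 bpm, a 10 bpm rise reads as +10 to 0 at Day 90 and +10 to -10 at Day 180. These figures rest on assumed linear slowing and a constant drug effect. The effect is small at Days 2 and 30 and in older children. It concerns about 3 completers and a descriptive secondary display, so it is a low-priority improvement. Individual age-referenced flags would be more useful than a mean.

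**What to change.** In SAP 4.3.1.2.3 and 4.3.1.2.4:

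1. Classify ECG heart rate and pulse as below, within or above age-specific limits at the child's age at each visit, using reference 8 or another named paediatric source. Use narrow or interpolated age bands so that an infant is not held in one wide band from baseline to Day 180.
2. Flag out-of-range records in the listings.
3. Tabulate shifts from baseline category to maximum and to minimum post-baseline category by age group, including unscheduled records, as SAP 4.3.1.2.2 does for laboratory data.
4. Show the age-referenced change beside the raw change, as a supplement only, with its imprecision stated.

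Optional: the same categories for PR and QRS; the Day 30 pre-dose to 6-hour change; and correcting the SAP's ECG timing sentence to include Day 1, as in Protocol Table 1, footnote n.

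**Cost.** SAP wording, one lookup table and a few small descriptive tables; no new data. Two downsides should be stated. Results depend on the reference: if its fall is wrong by 5 bpm, so is the age-referenced change. And 2% to 17% of children would exceed a 98th-centile upper limit at least once with no drug effect, so flags must be read against the baseline category.

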4.3.1.2.5 Physical Examination

Descriptive summaries for significant physical examination findings will be presented at each visit starting at baseline (as defined in Section 4.1.1.2). The supportive data listing of significant physical examination findings will be provided.

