### 1.3. Schedule of Activities

**Table 1: Schedule of Activities**

Study Day (window)	Screening	Treatment									EOS	ET
	-35 a to -1	1 b	2	15	30 (±2)	45	60 (±3)	90 (±3)	120 (±5)	150 (±5)	180 (±5)	-
At-clinic visit	X	X			X			X			X	
At-home telehealth visit c			X				X		X	X		
Telephone Contact d				X		X						
Procedure/Assessment												
Study intervention administration e		X			X		X	X	X	X		
Informed consent f	X											
Inclusion/exclusion criteria g	X	X										
Demographic/baseline characteristics	X											
Medical history	X											
PH disease history h	X											
Medication history i	X											
PH genotyping j	X											
Plasma oxalate sample	X										X	X
Spot urine collection k	X				X		X	X	X	X	X	X
Plasma PK sample l		X	X		X			X		X		X
Record fluid intake m	X				X		X	X	X	X	X	X
12-lead ECG n	X	X			X			X			X	X
Vital signs o	X	X	X		X		X	X	X	X	X	X
Physical examination p	X	X	X		X		X	X	X	X	X	X
Height and body weight q	X	X			X			X			X	X
Hematology r	X	X			X			X			X	X
Chemistry r	X	X			X		X	X	X	X	X	X
Coagulation s	X	X			X			X			X	X
eGFR t	X	X			X		X	X	X	X	X	X
Urinalysis u	X	X			X		X	X	X	X	X	X
Urine pregnancy test (WOCBP) v	X	X			X		X	X	X	X	X	X
Record stone events w		X	X		X		X	X	X	X	X	X
Kidney ultrasound x	X										X	X
Echocardiogram y	X										X	X
ADA sample	X				X			X		X	X	X

Study Day (window)	Screening	Treatment									EOS	ET
	-35 a to -1	1 b	2	15	30 (±2)	45	60 (±3)	90 (±3)	120 (±5)	150 (±5)	180 (±5)	-
At-clinic visit	X	X			X			X			X	
At-home telehealth visit c			X				X		X	X		
Telephone Contact d				X		X						
Procedure/Assessment												
Pediatric burden assessment z		X			X		X	X	X	X	X	X
PedsQL aa	X										X	X
Pharmacoeconomics bb	X							X			X	X
Record AEs and SAEs cc	X	X	X	X	X	X	X	X	X	X	X	X
Concomitant medications i		X	X		X		X	X	X	X	X	X

a An extra 14-day period will also be granted for participants who are required to repeat initially unanalyzable screening laboratory assessment samples or where lab samples are delayed due to technical/logistical issues at the central lab.

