- p Physical examination includes height/length, weight, inspection of injection site(s), and review of body systems. A full physical exam will be performed at Screening and Day 180 (or early termination). For at-home visits, the home-health nurse will provide in-person support to the Investigator in assessing the participant; height and weight will not be measured during at-home visits. The physical examination performed at other scheduled visits (Days 1 through Day 150) or unscheduled visits may be a brief or full physical examination at the Investigator's discretion. See Section 8.2.1 and Section 8.2.2.
- q The total dose will be based upon body weight recorded on study Day 1. For participants < 6 months of age at Screening, the dose will be adjusted at Day 90 to capture changes in weight; no other dose adjustments are allowed.
- r Blood samples for hematology and serum chemistry to be collected predose on dosing days. A single blood draw to be performed at other visits, as indicated. See Section 10.2 for the list of parameters.
- s Blood samples for coagulation studies to be collected predose. Coagulation panel will include prothrombin time (PT) and international normalized ratio (INR). Additional coagulation studies may be performed as clinically indicated.
- t Estimated glomerular filtration rate (eGFR) to be calculated only in participants aged 12 months and older, as described in Section 8.2.6.1.
- u Urinalysis with microscopy at Screening and as clinically indicated. Dipstick urinalysis may be performed at other scheduled visits. Collect sample for urinalysis before dosing. See Section 10.2 for parameters.
- v A positive urine pregnancy test will be confirmed with a serum pregnancy test. Administration of study intervention will be discontinued in any participant with a positive pregnancy test. A final pregnancy test will be conducted 2-3 weeks following the last dose of study intervention in any WOCBP who prematurely discontinues the study.
- w Parent(s)/legal guardian will report instances of renal stones requiring medical intervention, stone passage, and/or renal colic requiring medication (Section 8.1.3.1).
- x In the event of rescreening, if a participant had been screened for this study within the last 3 months and had ultrasound data sent to the central over-readers, repeat of the ultrasound will not be required during the rescreen.

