### 2.2.2. Nonclinical Overview

Nedosiran consists of the drug substance, nedosiran sodium (also known as DCR-L1360) in WFI. Nedosiran sodium is a synthetic double-stranded (hybridized duplex) RNA oligonucleotide conjugated to GalNAc aminosugar residues. After SC administration, the GalNAc sugars conjugated to the RNA oligonucleotide bind to ASGPR to deliver nedosiran sodium to hepatocytes. Nedosiran sodium reduces the level of mRNA encoding the dominant form of the LDH enzyme, specifically, the LDHA isoenzyme. Lactate dehydrogenase catalyzes the cytosolic conversion of glyoxylate to oxalate in the liver and this biochemical reaction is believed to be critical for oxalate generation for all 3 genetic forms of PH.

Inhibition of oxalate production has been accomplished in mouse models of PH1 and PH2 and in an indirect mouse model of PH3.

Nedosiran sodium was not associated with any adverse effects on cardiovascular, respiratory, or neurological function in cynomolgus monkeys when administered as a single SC injection at doses up to 300 mg/kg. In addition, in the pivotal repeat-dose toxicity studies (up to 6 months in mice and up to 9 months in monkeys), nedosiran sodium was well tolerated at dose levels up to 300 mg/kg in both mice and monkeys.

In definitive GLP fertility and early embryonic development and EFD studies in mice, no test-article-related toxicity was observed at dose levels up to 2000 mg/kg nedosiran sodium (highest dose administered) or 10 mg/kg of the mouse analog. In a preliminary, non-GLP, EFD study in rabbits (dose levels: 20 to 600 mg/kg), lower body weight gains in dams (with accompanying

lower food consumption) and embryofetal effects (higher litter proportions of postimplantation loss and lower numbers of live fetuses) were observed from the lowest doses. In addition, increased incidences of cardiovascular fetal malformations were noted. The human relevance of these contradictory observations in mice and rabbits is unclear, as nedosiran is not pharmacologically active in rabbits (i.e., no *Ldha* knockdown) and no such observations were noted in the mouse EFD studies with nedosiran or the pharmacologically active mouse analog.

See the Nedosiran IB for more details on the nonclinical studies.

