#### Age

1. Birth to 11 years of age inclusive, at the time of signing the informed consent.

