#### 9.4.3.2. Safety Endpoints

All safety analyses will be performed on the Safety Population. The incidence and nature of TEAEs and SAEs, along with change from Baseline in 12-lead ECG, physical examination findings, vital sign assessments, and clinical laboratory tests will be summarized.

Adverse events will be defined as treatment emergent if they have an onset or worsen in severity after a participant receives the study intervention. Treatment-emergent AEs will be summarized by SOC and preferred term according to the MedDRA. Treatment-emergent AEs will be further summarized by severity and relationship to study intervention. Adverse events leading to discontinuation, SAEs, and deaths will be summarized/listed.

Descriptive statistics will be provided for absolute values and changes from baseline in physical examination findings, vital sign measurements, ECGs, and clinical laboratory results at each timepoint.

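### Post-baseline height and weight, collected as safety assessments in children from birth to 11 years, reach only the listings: the SAP plans no summary of change and no age- and sex-standardised growth measure.

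*SAP*

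**What the plan says.** **Protocol.** Section 5.1 enrols children "Birth to 11 years of age inclusive, at the time of signing the informed consent". Weight, height and length have their own subsection, 8.2.1, under Safety Assessments (8.2), with calibrated equipment required. Table 1 gives height and body weight a separate row, marked at Screening, Day 1, Day 30, Day 90, Day 180 and early termination. Footnote p to the physical examination row says "Physical examination includes height/length, weight, inspection of injection site(s), and review of body systems". It adds that "height and weight will not be measured during at-home visits". Change from baseline in physical examination findings is a secondary safety endpoint (Section 3), and Section 9.4.3.2 says "Descriptive statistics will be provided for absolute values and changes from baseline in physical examination findings", together with vital signs, ECGs and laboratory results, at each timepoint.

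**SAP.** Section 4.1.4 summarises height/length, weight and BSA as demographics and baseline characteristics. Section 4.3.1.2.3 covers "Descriptive summaries for vital signs (systolic blood pressure, diastolic blood pressure, body temperature, pulse/heart rate, and respiration rate"; weight and height are not in that list. Section 4.3.1.2.5 says "Descriptive summaries for significant physical examination findings will be presented at each visit starting at baseline", supported by a listing of significant findings. Section 4.1.1.6 gives BSA and BMI formulas, but no post-baseline output uses them. Section 4.1.1.7 puts all collected data into listings and keeps data that the plan does not analyse out of tables and graphs. Section 4.8, on changes to protocol-planned analyses, reads as not applicable.

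**The concern.** Growth is a general safety measure in children who receive a systemic drug for six months, and the data to describe it are already being collected. The SAP turns the protocol's values and changes from baseline into a summary of significant findings, which depends on someone judging a finding significant. A slow drift in weight or height may never prompt that judgement at any single visit. It shows up when successive measurements are compared with what is expected for age and sex.

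There is no control arm to supply that expectation, and raw change does not supply it either, because nearly every child in this age range gains weight and height over six months. The SAP accepts this reasoning for its efficacy variable. Section 4.2.3 adds an analysis of the urinary ratio relative to an age-specific upper limit, to deal with natural maturation. Growth, where maturation matters at least as much, has no counterpart.

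At stake is whether the study report can describe growth at all, beyond leaving readers to work through individual listings.

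**Working it through.** No sample size, power or error rate is involved. The check is a count of measurements and a comparison of the two documents.

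**Step 1: scheduled measurements (Protocol Table 1, height and body weight row).**
- Screening, Day 1, Day 30, Day 90, Day 180 = 5 scheduled visits; with early termination, 5 + 1 = 6 marks.
- Screening and Day 1 are at or before first dosing and serve as baseline under SAP 4.1.1.2 = 2.
- Scheduled post-baseline measurements = 5 − 2 = 3 (Days 30, 90, 180).
- Days 2, 60, 120 and 150 carry no mark in this row, which fits the rule against measuring at home. If one of those visits takes place in clinic, footnote p could be read as implying an extra measurement; the count of 3 follows the marked row.

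**Step 2: every place where the SAP uses height, length, weight, BSA or BMI.**

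| SAP section | Use | Post-baseline summary of height or weight? |
|---|---|---|
| 4.1.4 | Height/length, weight and BSA as baseline characteristics | No |
| 4.1.1.6 | BSA and BMI formulas | No |
| 4.1.1.6, by reference to Protocol 8.2.6.1 | Height as an input to eGFR | No; eGFR is summarised, height is not |
| 4.3.1.2.3 | Five vital signs, neither variable included | No |
| 4.3.1.2.5 | Significant examination findings | No values or changes |
| 4.1.1.7 | Listings of all collected data | Listed, not summarised |

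**Step 3: result.**
- Post-baseline visits with a tabulated summary: 0 of 3.
- Post-baseline visits covered by listings: 3 of 3.
- Visits with a summary after the proposed change: 3 of 3, plus early termination where SAP 4.1.1.5 maps it to one of these visits.

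**Step 4: why raw change is not enough.** Let the expected six-month gain for a child's age and sex be g > 0, and let the child gain a fraction f of it, with 0 < f < 1. The raw change is f × g, which is positive for every such f. The shortfall is (1 − f) × g, and it can be seen only if g is known. With no control arm, g has to come from an external reference by age and sex, which is what a z-score uses. A child who holds position against the reference has a z-score change near 0; a child who falls behind has a negative change, even while gaining weight.

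**Step 5: how much data there would be.** The protocol synopsis aims for about 20 completers from about 25 enrolled: about 7 aged 6 to 11 years, 10 aged 1 to 5 years and 3 under 1 year. Over the four SAP age groups the average is 20 / 4 = 5 completers per group.

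**The case against.** **The listings carry the data.** With 20 to 25 children and three post-baseline visits, the listing is short and nothing is withheld. Growth failure that an investigator judged clinically significant could also appear as an adverse event (Protocol 10.4.1.1) or as a significant examination finding, and a Safety Review Committee reviews safety data periodically (Protocol 9.6). This stands against a stronger reading that a reader might infer, namely that impaired growth would go unreported. The documents do not support that reading. What is missing is a summary, not the data.

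**The mock TFL may contain a table.** SAP Section 1 leaves further output specifications to that document, which is not available here. That is possible. But Protocol 9.4 assigns the detailed description of the analyses to the SAP, and SAP 4.1.1.7 keeps data not analysed under the plan out of tables.

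**The protocol may never have promised this.** Section 8.2.2 defines the full and brief examinations by body system and lists neither height nor weight. Table 1 gives the two items separate rows, and the footnote to the height and weight row concerns dose calculation. Only footnote p places them inside the examination. This stands in part: a departure from Protocol 9.4.3.2 is arguable, not established. The gap does not depend on it, because variables that the protocol itself classes as safety assessments still have no post-baseline summary.

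**The SAP does use height after baseline.** This is correct: height enters the eGFR equation. It does not describe growth.

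**There is a nonclinical weight signal.** A reader might take the lower weight gain described in Protocol 2.2.2 as support for the point. It should not be used that way. It was seen in pregnant rabbits in a preliminary non-GLP study, with lower food consumption, in a species where the drug is not pharmacologically active, and the protocol calls its human relevance unclear.

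**The yield is small.** With about five completers per age group, six months of follow-up and no control arm, a shift in z-score cannot be attributed to the drug. This stands, and limits the table to description. The other safety summaries in this study have the same limit.

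**Conclusion.** The point holds as a reporting gap. Under the SAP text, height and weight at Days 30, 90 and 180 have no planned summary (0 of 3 visits), no change from baseline and no scale that accounts for age and sex; they would be found only in listings. A modest or gradual growth effect could be missed. A marked one could still surface through adverse events, significant examination findings or a reading of the listings.

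This rests on the SAP text being complete on the matter, since the mock TFL cannot be seen, and on the marked row of Table 1 for the visit count. It does not rest on any animal finding, on an assumed normal weight gain, or on a cut-off for z-score decline; the documents supply no basis for the last two. Whether Protocol 9.4.3.2 has been breached turns on whether footnote p or Section 8.2.2 governs, and need not be settled.

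The change is worth making. It does not affect the primary analysis, and it touches no dose or clinical rule.

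**What to change.** In SAP 4.3.1.2.3 or 4.3.1.2.5, add by-visit descriptive summaries for the Safety Population, by age group, of:
- weight-for-age and height/length-for-age z-scores, with change from baseline at Days 30, 90 and 180;
- weight in kg and height/length in cm, with the same changes, alongside.

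Name the growth standard in advance, one per age range if needed. State how age at each measurement is calculated, and how children who move from recumbent length to standing height are handled, since Protocol 8.2.1 makes that distinction at 24 to 36 months. Early termination measurements can follow the existing mapping in SAP 4.1.1.5.

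If the SAP can no longer be changed, put the same table in the clinical study report and identify it as unplanned, which SAP Section 1 allows.

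**Cost:** SAP wording, one derivation and one table. Age, sex, height/length and weight are already collected, so no visit, test or clinical procedure is added. The downside is limited interpretability: small groups, six months and no control arm, so the table describes growth and cannot attribute a change to treatment.
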